#### Creation of training materials

The training consisted of a training program including a training presentation and training brochure prepared by the researcher according to KMT variables by scanning the literature (Rogers W., 1983; Aydogdu et al., 2019; World Health Organization, 2021). The hypertension training presentation included the topics specified in Table 1 according to KMT variables;

**Table 2 Hypertension training topics**

Protection Motivation Theory Variables	Topics
	Definition of hypertension
Threat Assessment	Normal and high blood pressure values Importance of hypertension Unchangeable and changeable risk factors

	Complications of hypertension
	Being a treatable disease
	Treatment of hypertension
Coping Assessment	Patients' belief that they can control hypertension
	Importance of compliance with antihypertensive drug treatment
	Importance of compliance with healthy lifestyle behaviors
	Compliance with antihypertensive medication
Taking Action	Performing healthy lifestyle behaviors

The training presentation to be made aims to initiate threat assessment (perceived susceptibility, perceived severity) and coping assessment (response efficacy, self-efficacy, response costs) of the variables of KMT, to create protective motivation in patients and to ensure protective actions (medication compliance and gaining healthy lifestyle behaviors). The training brochure was prepared in line with the principles of theory to inform patients, to draw attention to the importance of the subject and to ensure that the given training is remembered later.

Expert opinion was sought in the evaluation of the content validity of the educational material (brochure and educational presentation) and SMS messages prepared for patients with hypertension. The Lawshe technique was used in the process of determining the content validity of the developed educational material and SMS messages. The prepared educational material (brochure and educational presentation) was presented to expert opinion with "expert evaluation forms". The expert opinions obtained in the last stage were evaluated and "content validity rates" and "content validity indices" were determined. Since all experts gave 2-3 suitability points in the suitability score, the content validity index of the educational material (brochure and educational presentation) was determined to be "1". When the critical values determined by Lawshe (1975) by considering 5 experts were taken into consideration, it was determined that the content validity of the developed educational material (brochure and educational presentation) was high since the content validity index was "1" ( $KGI \geq KGO$ ).

### Phone messages

SMS text messages based on KMT were prepared by the researcher in line with the literature (Aydogdu et al., 2019; World Health Organization, 2020; Turkish Endocrinology and Metabolism Association, 2022; World Health Organization, 2022; Republic of Turkey Ministry of Health, General Directorate of Public Health, 2021, 2023). A total of 24 text messages were designed according to KMT variables.

## **Implementation of the research**

The intervention consisted of two components and lasted 14 weeks (November 2023–March 2024). The first component was hypertension education based on KMT. The second component was sending regular KMT-based SMS messages aimed at reminding, encouraging and motivating patients to maintain medication adherence and healthy lifestyle changes.

### Applications made to the intervention group:

#### 1. Hypertension Education:

- Hypertension education was organized as a training session for each participant in the ASM training room and was carried out face to face.

- These trainings were carried out by the researcher. First, the researcher made a hypertension training presentation, then the subject was understood and reinforced with questions and answers. The training period lasted 30-40 minutes for each participant.

- First, the training plan was explained, and their opinions were taken regarding the application day and time. In case of any unexpected situation, an attempt was made to determine a different day of the week with the patients for the make-up training session.

- PowerPoint presentation and training brochures prepared within the scope of the research were used as training materials.

#### 2. Sending SMS Message:

Participants received SMS messages prepared with expert opinions after the approval of the ethics committee twice a week (Tuesday-Friday) for 12 weeks to remind them of the topic after the last training session. 24 different SMS messages prepared according to the KMT variables in order to create protection motivation in hypertensive individuals were sent to the participants in the intervention group twice a week (Tuesday-Friday) between 09:00-17:00 for 12 weeks after the last training session.

### Applications made to the control group:

The control group was not subjected to any intervention by the researcher during the study. The control group was given an information note and brochure prepared within the scope of the research along with the collection of post-test data.

## **1.12. Variables of the Study**

Dependent variables: Antihypertensive drug treatment compliance scale score averages, healthy lifestyle behaviors scale score averages, SBP and DBP values.

Independent variables: Nursing interventions based on Protection Motivation Theory.

### **1.13. Limitations of the Study**

- The study was limited to only patients diagnosed with hypertension who were followed up at the 7th ASM affiliated to the Karaman Provincial Health Directorate during the relevant dates.
- The fact that the study was conducted over a six-month period is also a limitation of our study. However, despite this, the group\*time effect was evaluated during the analysis phase and as a result, it was shown that the nursing interventions created a statistically significant change during the six-month application period.
- The researcher could not be blinded due to the nature of the study.
- There was an appointment for another time to provide individual education to the patients in the intervention group.

### **1.14. Strengths of the Research**

- The results of this research have shown that remote health services can be provided to hypertensive individuals via mobile phones, and in this respect, it has contributed to the literature on the use of digital health technologies.
- It is thought that the research will contribute to evidence-based nursing due to the fact that the research was conducted in a randomized controlled manner, blind technique was used, and ITT analysis included effect size and confidence intervals.
- The fact that the nursing interventions (SMS message and education) applied in the research were free, easy and simple shows that they are feasible in terms of cost.
- In addition, the use of theory in the foundation of nursing interventions in this research is one of the strengths of the research.

### **1.15. Analysis of Data**

In this study, data analyses were performed using the IBM SPSS Statistics Standard Concurrent User V 26 (IBM Corp., Armonk, New York, USA) program. Descriptive statistics were given as number of units (n), percentage (%), mean (X), standard deviation (SS), median (M), minimum (min) and maximum (max) values. Reliability for scales and their sub-dimensions was examined using Cronbach's Alpha coefficient. Scales with a Cronbach's Alpha coefficient above 0.60 were considered reliable. Skewness and kurtosis values were examined to test whether the data met the assumption of normality. In the decision phase, if the absolute skewness (Skewness) value is below  $\pm 2.0$  and the kurtosis value is below 7.0, it is decided that the data is normally distributed (Kim, 2013). In the comparison of numerical descriptive characteristics of the patients between groups, independent sample t test was used, and in the

comparison of categorical descriptive characteristics between groups, chi-square tests (Pearson chi-square/Fisher exact test) were used. In the comparison of variables in the groups according to the follow-up times, mixed order analysis of variance (ANOVA) was used. Bonferroni correction was applied in the comparison of main effects in the analyses. The value of  $p < 0.05$  was considered statistically significant. Intention to treat (ITT) analysis was performed in the evaluation of the data. Since it was not possible to reach the 7 individuals who left during the research process for the ITT analysis of this study, the post-tests were filled by repeating the answers given by the patients in the pre-tests, and the missing data were completed in this way.

### **1.16. Ethical Dimension of the Research**

Before the research, ethical approval was obtained from Necmettin Erbakan University Health Sciences Scientific Research Ethics Committee with the decision number 404 dated 05.04.2023 and written permission was obtained from Karaman Provincial Health Directorate. This research was conducted in accordance with the Helsinki Declaration Principles. Before filling out the questionnaire form, participants were informed about the research and their written and verbal consents were obtained. Necessary permissions were obtained via e-mail from the authors who adapted the scales into Turkish for scale use.

**THE EFFECT OF NURSİNG INTERVENTİONS BASED ON CONSERVATİON
MOTİVATİON THEORY ON DRUG ADHERENCE AND HEALTHY LİFESTYLE
BEHAVİORS İN PATİENTS WİTH HYPERTENSİON: A RANDOMİZED
CONTROLLED STUDY**

NCT05995977

Document Date: 20 June 2024

Statistical Analysis Plan

In this study, data analysis was performed using the IBM SPSS Statistics Standard Concurrent User V 26 (IBM Corp., Armonk, New York, USA) program. Descriptive statistics were given as unit number (n), percentage (%), mean (X), standard deviation (SS), median (M), minimum (min) and maximum (max) values. Reliability for scales and their sub-dimensions was examined using Cronbach's Alpha coefficient. Scales with a Cronbach's Alpha coefficient above 0.60 were considered reliable. Skewness and kurtosis values were examined to test whether the data met the assumption of normality. In the decision stage, if the absolute skewness (Skewness) value is below ± 2.0 and the kurtosis value is below 7.0, it is decided that the data is normally distributed (Kim, 2013). Accordingly, the skewness and kurtosis values of the variables used in the study are given in Table 3.6 and it was found that the data were suitable for normal distribution. Independent sample t test was used to compare numerical descriptive characteristics of patients between groups, and chi-square tests (Pearson chi-square/Fisher exact test) were used to compare categorical descriptive characteristics between groups. Mixed order analysis of variance (ANOVA) was used to compare variables according to follow-up times in groups. Bonferroni correction was applied to compare main effects in the analyses. A p value of <0.05 was considered statistically significant.

Intention to treat (ITT) analysis was performed in the evaluation of the data. ITT is a basic method used in maintaining randomization and preventing bias in case of withdrawal from the study. The approach to be applied when handling missing data varies according to whether the data is discrete or continuous. The most common method used in filling in missing data in continuous data is to fill in the last observed data by repeating the outcome measurements (Last Observation Carried Forward). Since it was not possible to reach 7 individuals who dropped out during the research process for the ITT analysis of this study, the post-tests were filled in by repeating the answers given by the patients in the pre-tests and the missing data were completed in this way. A summary of the statistics used in this study is shown in Table 1.

Table 1. Statistics used in the study (n=78).

Evaluated statistics	Statistical methods
Normal distribution	Skewness and kurtosis values
In comparing numerical descriptive characteristics between groups	Independent Sample t Test
In comparing categorical descriptive characteristics between groups	From chi-square tests (Pearson chi-square/Fisher exact test)
In comparing variables in groups according to follow-up times	Mixed order analysis of variance (ANOVA)
In comparing main effects in analyses	Bonferroni correction
Reliability for scales and their sub-dimensions	Cronbach's Alpha coefficient
In evaluating missing data	intention to treat (ITT) analysis

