#### 1.9.8. Measuring results

The primary outcomes of this study were the level of compliance with antihypertensive drug treatment and healthy lifestyle behaviors. Secondary outcomes were changes in SBP and DBP levels. Primary and secondary outcomes were assessed at the first month ( $T_0$ ), the end of the third month ( $T_1$ ), and the end of the sixth month ( $T_2$ ).

Preliminary application: After obtaining permissions for the study, 8 hypertensive individuals (10% of the sample) who met the inclusion criteria were provided with data collection tools and an evaluation of the clarity of the questions; no problems were encountered. These 8 individuals were excluded from the sample.

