## **1.10. Data Collection**

Pre-test forms were administered to hypertensive individuals who agreed to participate in the study in November 2023, T1 data in March 2024, and T2 data in May 2024 at the ASM and were filled out by the researcher according to the hypertensive individual's self-report.

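### The group-by-time test is tied to no visit and cannot show an effect at month 6; baseline-adjusted contrasts at T1 and T2 would, usually with better precision

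*SAP*

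**What the plan says.** The SAP states that "Mixed order analysis of variance (ANOVA) was used to compare variables according to follow-up times in groups", and its Table 1 repeats this as the only method for comparing outcomes over time. Protocol section 1.15 gives the same analysis. The only follow-up comparison named is for main effects: "Bonferroni correction was applied to compare main effects in the analyses" in the SAP and "Bonferroni correction was applied in the comparison of main effects in the analyses" in the protocol.

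Outcomes are measured at T0, T1 and T2. Section 1.10 dates the follow-ups: "T1 data in March 2024, and T2 data in May 2024 at the ASM". Under the implementation heading, "The intervention consisted of two components and lasted 14 weeks", running from November 2023 to March 2024.

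Section 1.9.8 says "The primary outcomes of this study were the level of compliance with antihypertensive drug treatment and healthy lifestyle behaviors", without a primary visit. Section 1.13 refers to the group-by-time effect and concludes that "it was shown that the nursing interventions created a statistically significant change during the six-month application period". Section 1.14 says that the "ITT analysis included effect size and confidence intervals", but neither document says for which contrast or visit.

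No sentence lists the levels of the ANOVA. That T0 is one of them is inferred from the three measurement times and the absence of any covariate; no other reading fits.

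**The concern.** The useful questions here are how the arms differ once the intervention has ended, and whether that difference is still there at month 6. T1 coincides with the end of the intervention and T2 comes about two months later, so T2 is a follow-up measurement.

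A group-by-time F over three visits says only that the arm difference is not constant across T0, T1 and T2. It does not say at which visit the arms differ. The two main effects do not help. The time effect pools the arms, and the group effect pools the visits, including T0, when no effect can exist.

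At stake are two things. A month-6 claim might rest on a difference that was present only at T1. Precision is also given up by not using the T0 value as a covariate.

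**Working it through.** **The plan's own figure.** Section 1.3 of the protocol gives 35 per group for a Mann-Whitney test with alpha 0.05, effect size 0.90 and power 95%. A two-sided non-central t calculation with the normal-parent efficiency 3/π gives power 0.946 at 34 per group and 0.952 at 35. Then 35/0.90 = 38.9, rounded up to 39. Both stated figures reproduce. They were derived for a two-group comparison, not for the group-by-time term.

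**Inputs.** n = 39 per arm (enrolled) or 35 (calculated) and d = 0.90 come from section 1.3. Assumed, because the documents give no value: within-person correlation r = 0.3/0.5/0.7, equal at all pairs of visits; unit SD; a smaller effect d = 0.5. Tests are two-sided at 5%.

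**Group-by-time.** With arm differences D at T0, T1, T2, the non-centrality is λ = (n/2)·Σ(D − mean D)²/(1 − r), on 2 and 2(2n − 2) df.

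- Sustained (0, d, d): mean 2d/3, so Σ = (4/9 + 1/9 + 1/9)d² = (2/3)d².
- Vanished (0, d, 0): mean d/3, so Σ = (1/9 + 4/9 + 1/9)d² = (2/3)d².

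The two sums are equal, so power is identical at every r. For d = 0.5, n = 39, r = 0.5: λ = 19.5 × 0.1667/0.5 = 6.5, giving power 0.61 for either pattern.

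**Comparators for a sustained effect.**

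- ANCOVA at T2: standardised effect d/√(1 − r²), 2n − 3 df.
- ANCOVA on the T1/T2 mean: d/√((1 + r)/2 − r²), 2n − 3 df.
- Group main effect: (2d/3)/√((1 + 2r)/3), 2n − 2 df. Averaging in T0 shrinks an equal T1/T2 effect to two thirds.

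| Power, r = 0.3/0.5/0.7 | d = 0.90, 35 per arm | d = 0.5, 39 per arm |
|---|---|---|
| Group-by-time, sustained or vanished | 91/98/99.9% | 47/61/84% |
| ANCOVA at T2, sustained | 97/99/99.9% | 63/71/86% |
| ANCOVA on T1/T2 mean, sustained | 99.9% or more | 83/87/95% |
| Group main effect, sustained | 92/86/79% | 51/43/37% |

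If the effect has vanished by T2, ANCOVA at T2 rejects at its nominal 5%.

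**Precision.**

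- At T2 the change-from-T0 variance is 2(1 − r) and the ANCOVA variance 1 − r². Their ratio is 2/(1 + r) = 1.54/1.33/1.18.
- For the T1/T2 mean the variances are (1 + r)/2 + 1 − 2r and (1 + r)/2 − r², with ratio 1.88/1.50/1.25.
- The 95% CI half-width at T2 is 1.992·√(2·variance/39). This gives 0.43/0.39/0.32 SD for ANCOVA and 0.53/0.45/0.35 SD for change.

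**Exceptions (d = 0.5, 39 per arm).** At r = 0.1 the group main effect is ahead of ANCOVA at T2 (63% against 59%). At r = 0.8 group-by-time is marginally ahead (95.6% against 95.3%). ANCOVA on the T1/T2 mean has 84% and 99% there.

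**Adherence scale.** Entry requires a score of 8 or above on a 1–13 scale, which truncates T0. Six scenarios were simulated, with 4,000 trials each. Scores were rounded and clipped to 1–13, with 39 per arm, assumed SD 2.5, population mean 6–8, retest correlation 0.5–0.7 and d = 0.5 of the post-entry SD. Power was 55–68% for the Greenhouse-Geisser-corrected group-by-time test, 60–69% for ANCOVA at T2 and 77–83% for ANCOVA on the T1/T2 mean. The gains over group-by-time are about 0–5 points and 14–23 points respectively.

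**The case against.** The case for the plan has several parts.

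- **Other comparisons may exist.** The protocol abstract reports directional differences between arms after the interventions, and section 1.14 mentions effect sizes and confidence intervals. An omnibus F alone cannot give direction, so between-arm comparisons may have been run under the translated phrase about main effects. This is possible, but the abstract names no visit or contrast either, so the reader still cannot tell what was estimated.
- **Section 1.13 claims change during six months, not an effect at month 6.** On a literal reading that is fair, and no persistence objective is written down. The wording nonetheless treats six months as the period of application, when the intervention lasted 14 weeks.
- **The mixed ANOVA is valid under randomisation.** Agreed. The complaint is about the target and the precision, not bias.
- **The efficiency gain is small where it counts.** At d = 0.90, and for the T2 contrast on the adherence scale, this stands. The larger gain belongs to the T1/T2 mean, which cannot show persistence: for (0, d, 0) it still equals d/2. That is why T2 must be reported separately.
- **The variance comparator is not in the plan.** The change-from-T0 contrast is used as a benchmark only. That ANCOVA's variance is no larger is a large-sample statement; at very low r, estimating the slope costs slightly.
- **Imputation is not modelled.** Post-tests for 7 of 78 participants (9.0%) were copied from the pre-test, which alters both r and the effect. The figures are therefore approximate; the equality of the two patterns is not affected by the value of r.

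**Conclusion.** The concern holds. As written, the plan contains no between-arm estimate at T1 or T2, and the test cited in section 1.13 cannot distinguish a lasting effect from one that has gone by month 6. That result is algebraic; it assumes equal arms at T0 and, for the power figures, a common correlation between visits.

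The loss of efficiency is secondary and depends on assumptions. At d = 0.5 and r = 0.3 to 0.7, ANCOVA at T2 gains about 16 to 2 percentage points over group-by-time. At the planned d of 0.90 with 35 per arm it gains about 6 points at r = 0.3 and almost none at r = 0.7. The change should be made, chiefly for interpretation.

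**What to change.** For each outcome, fit a model to T1 and T2 with the T0 value as covariate plus group, visit and group × visit, treating a participant's two measurements as correlated. Report the adjusted group difference at T2, at T1 and for the T1/T2 mean, each with a 95% CI. State that T1 is the end of the intervention and T2 is follow-up after it. Base any six-month statement on the T2 contrast. Treat the group and time main effects and within-arm changes as descriptive. If between-arm comparisons at T1 and T2 were already run, name them in the SAP.

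The SAP is dated 20 June 2024, after T2 collection in May 2024, so the model must be labelled post hoc and shown beside the group-by-time result. The cost is one additional model per outcome on existing data in the same software, plus SAP wording. No new participants or visits are needed. The price in power is at most slight: the T2 contrast can fall a little behind another ANOVA term at extreme correlations.

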**NCT05995977**

**Document Date: 1 August 2023**

## ABSTRACT

Hypertension is a major global public health problem. For success in the prevention and management of hypertension, it is necessary to ensure that patients receive timely and accurate diagnosis, acquire healthy lifestyle habits, start antihypertensive drug treatment on time, and ensure compliance with treatment. The study was conducted in a pre-test-post-test parallel group randomized controlled design in order to determine the effects of nursing interventions consisting of hypertension education and sending short messages, created by utilizing Rogers' Protective Motivation Theory (CMT), on medication compliance and healthy lifestyle behaviors for hypertensive individuals. The study was conducted at Family Health Center No. 7 in the center of Karaman province between November 2023 and May 2024. The study group included individuals between the ages of 40 and 59, who had low compliance with treatment, had no communication problems in terms of hearing, vision, and understanding, used a mobile phone to receive the short message to be sent by the researcher, and were diagnosed with primary hypertension. The study was conducted with 78 hypertensive individuals, 39 in the intervention group and 39 in the control group, calculated with 95% power. Ethics committee, institution, scale use permission and written consent of the participants were obtained before the study. Data were collected at the beginning ( $T_0$ ), at the end of the third month ( $T_1$ ) and at the end of the sixth month ( $T_2$ ) using the Personal Information Form, Antihypertensive Drug Treatment Adherence Scale, Healthy Lifestyle Behaviors Scale, Blood Pressure Monitoring Form. Multiple nursing interventions consisting of hypertension education, brochure and short message created by using Rogers' KMT were applied by the researcher for 14 weeks. The control group was expected to continue their routine treatment for six months and no intervention was applied. Pre-test, interim and post-test measurements were collected by the researcher using the face-to-face interview method. Blindness was applied in terms of statistics expert and reporting. In the analysis of data, t test, chi-square test (Pearson chi-square/Fisher exact test) were used in independent groups, mixed order analysis of variance (ANOVA) was used in comparing variables according to follow-up times in groups, and Bonferroni correction was used in comparing main effects in the analyses. After the applied nursing interventions, a significant difference was found between the total mean scores of Antihypertensive Drug Treatment Adherence Scale, Healthy Lifestyle Behaviors Scale and systolic blood pressure and diastolic blood pressure values of the intervention and control groups ( $p<0.05$ ). After the nursing interventions, the total mean scores of Antihypertensive Drug Treatment Adherence Scale and systolic blood pressure and diastolic blood pressure values of hypertensive

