### **1.3. Universe of the Research and Study Group**

**Universe:** The research population consists of 407 individuals with primary hypertension between the ages of 40-59, registered in Family Health Center No. 7.

**Working group:** In this study, the sample size was calculated before the data collection stage at a 95% confidence level using the "G. Power-3.1.9.2" program to determine the study group. Özpancar's (2013) study, which examined the effect of education given by nurses on

treatment compliance in patients with hypertension, was used for the calculation. According to the data obtained from the study in question, the sample number required for the study was determined as 35 for each group (35 people for the control group + 35 people for the experimental group; 70 people in total) by taking the alpha value of 0.05 for the Mann Whitney U test, the effect size of 0.90, and the theoretical power as 95%. The 10% loss rate in previous studies (Zahr et al., 2019; Dağıstan Aköz, 2022) was taken into account and it was decided to include a total of 78 participants, 39 in each group.

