## 1.7. Reasons for Leaving the Study

The study started with a total of 78 participants and ended with “three” from the intervention group and “four” from the control group. After the participants left, the study was completed with a total of 71 patients, 36 from the intervention group and 35 from the control group. The patients who left the study stated the following reasons for leaving the study: “I am very busy, I can no longer spare time for your work” (n=3), “My blood pressure is no longer high, I am better, I want to leave your intervention” (n=1), “I cannot walk or diet, I cannot lose weight, I do not want to fill out your survey” (n=1) (5 patients in total). In addition, a total of 2 patients had to be removed from the study because the phone numbers they provided could not be reached by the researcher.

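### The seven dropouts' missing follow-ups are filled with pre-test answers and no sensitivity analysis is described, so the statement that attrition bias was controlled is not supported; the likely effect is modest

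*SAP*

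**What the plan says.** The SAP, in its paragraph on intention to treat, states that "the post-tests were filled in by repeating the answers given by the patients in the pre-tests". Protocol section 1.15 gives the same rule: "the post-tests were filled by repeating the answers given by the patients in the pre-tests". The SAP table of methods is headed "Statistics used in the study (n=78"), and mixed ANOVA is the only method listed for comparing outcomes over follow-up. Its entry for missing data is simply intention to treat. Neither document describes a completer analysis, a model on observed values, multiple imputation or a shift analysis.

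Protocol section 1.7 reports 36 intervention and 35 control completers, so 3 and 4 were lost. The reasons given are lack of time (three people, "I am very busy, I can no longer spare time for your work"), blood pressure no longer high (one), inability to walk, diet or lose weight (one), and unreachable telephone numbers (two).

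Section 1.8 says that intention-to-treat analysis was applied to prevent attrition bias and concludes that this bias was controlled. Section 1.14 lists that analysis, with effect sizes and confidence intervals, among the study's strengths.

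**The concern.** Intention to treat settles who is analysed and in which arm. It does not say what the missing outcomes would have been. Copying the pre-test forward supplies an answer, zero change for every dropout, and the ANOVA treats that answer as data.

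The assumption is doubtful in two places. One person left because their blood pressure was no longer high, which conflicts with entering their baseline blood pressure at follow-up. For adherence, everyone was enrolled on a score of 8 or above on a 1 to 13 scale where high is poor (protocol Table 1 and sections 1.6 and 1.9.3). Some movement toward the mean is therefore plausible in both arms without any treatment effect.

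At stake are the size of the group differences, the width of their intervals, and whether the assurance in section 1.8 can stand. The plan gives a reader no way to see how far any outcome depends on the seven.

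**Working it through.** **Inputs from the documents.** 39 randomised per arm; 36 and 35 completers; a planned loss of 10%; and for planning "the effect size of 0.90, and the theoretical power as 95"%. No outcome means or SDs are given, so the size has to be worked in SD units.

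**1. The plan's own figure.** A two-sample t calculation with the Mann-Whitney efficiency 3/π, d = 0.90, two-sided alpha 0.05 and power 95% gives 35 per group (power 0.952). This matches section 1.3. Allowing for loss, 35/0.90 = 38.9, so 39. Actual loss is 7/78 = 9.0% (3/39 = 7.7% and 4/39 = 10.3%), within plan, and the completers still meet 35 per group.

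**2. Effect of the fill on the estimate.** Suppose dropouts would have changed like completers. Let the intervention arm change by D and controls by kD.

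- True difference: (1 − k)D
- Filled difference: (36/39 − 35k/39)D
- Bias: (4k − 3)D/39

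| k | Filled ÷ true | Effect |
|---|---|---|
| 0 | 0.923 | shrinks 7.7% |
| 1/3 | 0.936 | shrinks 6.4% |
| 1/2 | 0.949 | shrinks 5.1% |
| 3/4 | 1.000 | none |

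Above k = 3/4 the bias favours the intervention. If both arms change by 1 SD (k = 1), it is 1/39 = 0.026 SD.

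**3. Effect on intervals.** Simulation, 20,000 trials per setting: 39 per arm, normal data, SD 1, equal correlation r between visits, and 3 and 4 random dropouts with T0 only. The correlations and the random dropout are assumptions. The contrast is T2 − T0, with changes of 0.9 SD against 0.

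| r | Half-width: fill | Completers | Likelihood | Coverage: fill | Coverage: likelihood |
|---|---|---|---|---|---|
| 0.3 | 0.513 | 0.558 | 0.552 | 94.5% | 95.1% |
| 0.5 | 0.436 | 0.472 | 0.470 | 94.1% | 95.2% |
| 0.7 | 0.341 | 0.365 | 0.365 | 93.6% | 95.1% |

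The fill averages 0.83 for a true 0.90 (0.90 × 36/39 = 0.83), with intervals about 7 to 8% narrower than completers'. The likelihood estimate averages 0.90. The narrowing is not universal. If controls change half as much as the intervention arm, the filled interval ranges from 3.6% narrower to 3.2% wider, with coverage of 96.0 to 96.8%.

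**4. Type I error.** With no true difference, the group × time test on filled data rejected in 3.9 to 5.1% of trials.

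**5. Sensitivity to the seven.** Moving each dropout's value by s against the intervention, in opposite directions by arm, moves the difference by 3s/39 + 4s/39 = 7s/39 = 0.18s. That is 0.18 per adherence point, 1.79 per 10 lifestyle points and 0.90 per 5 mmHg. The shift needed to lose significance is (difference − likelihood half-width)/(7/39). At 0.90 SD, taken to apply to T2 − T0, this is (0.90 − 0.552)/0.1795 = 1.9 SD at r = 0.3 and (0.90 − 0.365)/0.1795 = 3.0 SD at r = 0.7. At an assumed 0.6 SD it is 0.3 to 1.3 SD.

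**The case against.** The strongest reply is that little turns on this. Loss is small, nearly balanced and within plan. The fill usually pulls the difference toward zero, type I error holds, and in simulation the rejection rates of the filled and completer analyses differ by no more than about 1.2 percentage points. At the only effect size in the documents, every dropout would have to move by about 2 to 3 SD in the unfavourable direction to change the conclusion. Smaller effects such as 0.6 SD are assumptions. All of this stands, and it limits the severity. It does not make the section 1.8 statement correct. The section 1.3 effect comes from one study of treatment compliance, and no planning effect is given for lifestyle behaviours or blood pressure.

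A reader might infer further defects that the documents do not support:

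- *The visits filled are unclear*, because the abstract separates "Pre-test, interim and post-test measurements were collected by the researcher using the face-to-face interview method". A conventional three-visit mixed ANOVA at n=78 needs complete rows, which implies that every missing follow-up was filled.
- *The fill departs from the method cited*, to "fill in the last observed data by repeating the outcome measurements (Last Observation Carried Forward"). For anyone lost before T1 the two coincide. Timing may be in the flow chart, which is not shown.
- *The justification conflicts with section 1.7*, since "Since it was not possible to reach the 7 individuals who left during the research process" is said of all seven and only two had unreachable numbers. The ordinary reading is that follow-up data could not be obtained from people who had left.
- *Two reasons contradict the fill.* Only the blood-pressure one clearly does. Being unable to walk or diet is compatible with no lifestyle change.

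**Conclusion.** The point holds as a minor one. A single pre-test fill, analysed as observed and with no sensitivity analysis described, does not support the statement that attrition bias was controlled. The expected distortion is modest: a 5 to 8% shrinkage of the difference when controls change up to half as much as the intervention arm, none at three quarters, and slight exaggeration beyond. With controls unchanged, coverage is about 94%. These sizes assume that dropouts resemble completers, that dropout is random and that correlations lie between 0.3 and 0.7.

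A reader might infer that the reported differences are wrong or that benefit has been overstated. The documents do not show that: in most of the scenarios examined the fill works against the intervention. Nor should the fill simply be called conservative, because the direction depends on how much controls changed.

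**What to change.** 1. In the SAP and protocol section 1.15, add a likelihood-based repeated-measures model (group, time, group × time) on all observed T0, T1 and T2 values of all 78 participants in their assigned arms, with no single imputation. Label it as added after results were known, since the protocol abstract already reports them. Present it beside the original fill analysis.
2. That model assumes values are missing at random, so add one simple shift check per outcome. Move the seven dropouts' missing values against the intervention over a plausible range, and say whether the conclusion changes. Running shifts out to the scale limits is more than seven dropouts need.
3. In section 1.8, replace the statement that attrition bias was controlled with one saying that the result's dependence on the seven dropouts was examined in these analyses.

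The cost is a little more analysis on data already held, a post hoc label, and usually slightly wider intervals than the fill gives. In the simulations they were about 7 to 8% wider if controls do not change (for example 0.552/0.513 = 1.076), and 3.0 to 5.7% wider if controls change one third as much as the intervention arm.
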